3.2 Subgroups/Stratifications

There will be eight strata according to gender, smoking status and baseline mean whole mouth MGI score (Low \leq 2.0/High $>$ 2.0):

- Stratum 1: Male, Smoker, Baseline MGI \leq 2.00
- Stratum 2: Male, Smoker, Baseline MGI $>$ 2.00
- Stratum 3: Male, Non-smoker, Baseline MGI \leq 2.00
- Stratum 4: Male, Non-smoker, Baseline MGI $>$ 2.00
- Stratum 5: Female, Smoker, Baseline MGI \leq 2.00
- Stratum 6: Female, Smoker, Baseline MGI $>$ 2.00
- Stratum 7: Female, Non-smoker, Baseline MGI \leq 2.00
- Stratum 8: Female, Non-smoker, Baseline MGI $>$ 2.00.

3.3 Timepoints and Visit Windows

Deviations from the scheduled assessment times should be avoided or kept to a minimum as possible. Any deviation will be noted in blind data review meeting (BDRM) before database lock and subjects may be considered for exclusion from the per protocol population.

The following are the assessment time windows.

Visit	Time window
Visit 2	1-28 days after Visit 1. Visit 2 is baseline and counted as Day 0.
Visit 3	42 ± 3 Day
Visit 4	84 ± 3 Days

4 Data Analysis

Data analysis will be performed by Syneos Health. Prior to database closure a Blind Data Review Meeting (BDRM) will be conducted in which various aspects of the trial will be discussed and agreed. The statistical analysis software used will be SAS version 9.4 or higher.

Except as described below, all listings will be produced for all randomized subjects.

4.1 Populations for Analysis

Unless otherwise specified, Tables described in this section will be produced for all randomized subjects.

4.1.1 Subject Disposition

Screen failures will be defined as subjects who consent to participate in the study but are never subsequently randomized. A summary will be provided of the number of subjects screened and the number of screen failures.

Subject disposition will be summarised as the number and percentage of subjects (out of the number of randomized subjects) who complete the study, with the number who discontinue broken down by reason for discontinuation ([Table 14.1.1](#)). The table will also summarise the number and percent of subjects assigned to each analysis population (defined in Section 2.1.3). The summary will be presented by treatment and overall.

Subject disposition will be listed for randomized subjects ([Listing 16.2.1.1](#)) and non-randomized subjects ([Listing 16.2.1.2](#)) separately.

4.1.2 Protocol Deviations

Protocol violations will be tracked by the study team throughout the conduct of the study. All violations will be reviewed prior to unblinding and closure of the database to ensure all important violations are captured and categorized.

Major violations identified as liable to influence the efficacy outcome will include but not necessarily limited to those listed below:

- Major violation of inclusion/exclusion criteria
- Significant non-compliance with assigned product regimen (e.g., under- or over- use)
- Significant non-compliance with the visit schedule
- Use of prohibited treatment or medication before or during the study

Further violations liable to influence the efficacy outcome will be given in the “Review Listing Requirement (RLR)” document and major violations will be identified in blinded data review stage. The number and percentage of subjects with any major protocol deviations and with each type of major protocol deviations will be presented by treatment (Table 14.1.2) and listed (Listing 16.2.2.1). Any minor protocol deviations will be listed similarly (Listing 16.2.2.2).

4.1.3 Analysis Populations

Six analysis populations are defined.

Population	Definition / Criteria	Analyzes Evaluated
All Screened Subjects	All subjects who are screened	Disposition
Randomized	All subjects who are randomized and may or may not receive the application of the study products.	Protocol deviations
Safety	Safety population includes all subjects who are randomized, administered a study product at least once.	Safety analysis
Intent-to-Treat (ITT)	The ‘Intent to treat’ (ITT) population includes all subjects who are randomized, administered the study product at least once and provide at least one post-baseline assessment of efficacy.	Efficacy analysis
Per-Protocol (PP)	The Per Protocol (PP) population is a subset of the ITT population which excludes subjects with a protocol violation that is deemed to affect efficacy for all efficacy	Efficacy analyzes for BI score and number of bleeding sites and MGI score.

Population	Definition / Criteria	Analyzes Evaluated
	assessments. Subjects with a protocol violation that is deemed to affect efficacy for only some (but not all) of the efficacy assessments will be part of the PP population. PP analyzes will use only the data considered unaffected by protocol violations.	
Repeatability population for modified gingival index (MGI) assessment	All subjects who have an initial and a repeat assessment on MGI.	Repeatability analysis
Repeatability population for plaque index (PI) assessment	All subjects who have an initial and a repeat assessment on PI.	Repeatability analysis

The primary population for assessment of efficacy will be the ITT population. A PP analysis will be performed on the primary variable only if more than 10% of the subjects in the ITT population are excluded from the PP population.

The numbers of subjects excluded from each population broken down by the reason for exclusion will be presented ([Table 14.1.2](#)). Subjects excluded from any of the analysis populations will be listed ([Listing 16.2.3.1](#)).

4.2 Subject Demographics and Other Baseline Characteristics

Demographic and baseline characteristics summaries will be produced for the ITT.

4.2.1 Demographic Characteristics

Categorical demographic variables include year of birth, gender and race. These variables will be summarised by the number and percentage of subjects with each relevant characteristic ([Table 14.1.3.1](#) for the Safety population, [Table 14.1.3.2](#) for the ITT population and [Table 14.1.3.3](#) for the PP population if PP analysis is performed). Age will be summarised by the mean, standard deviation (SD), median, minimum and maximum values. Baseline stratification will also be summarised by the number and percentage of subjects in each stratum. All summaries will be presented by treatment, and overall. All demographic information will be listed for randomized subjects ([Listing 16.2.4.1](#)).

4.2.2 General Medical History

Medical history data will be listed in [Listing 16.2.4.2](#) with start date and end date or ongoing at the start of study drug. A data listing will also be produced for evaluation of protocol violations at the blinded data review stage.

4.3 Treatments (Study Product, Rescue Medication, other Concomitant Therapies, Compliance)

4.3.1 Study Product Compliance and Exposure

Brushing compliance (using study products twice daily) will be listed and checked at the blinded data review stage for evaluation of protocol deviations.

4.3.2 Prior and Concomitant Medication

Prior and concomitant medication/non-drug treatments data will be listed ([Listing 16.2.5.1](#) for prior medication, [Listing 16.2.5.2](#) for concomitant medication/non-drug treatments). Prior medications are defined as those stopped before the first administration of the study products. Concomitant medications are defined as those ongoing or started on or after the first administration of the study products.

4.4 Analysis of Efficacy

Statistical testing of all endpoints in this study will be conducted at unadjusted two-sided significant level of 0.05. The null and alternative hypotheses are

- H_0 : there is no difference between treatment groups;
- H_a : there is a difference between treatment groups.

4.4.1 Primary Efficacy Endpoint

4.4.1.1 Primary Efficacy Endpoint Definition

The bleeding index (BI) will be assessed on the facial and lingual gingival surfaces of each scorable tooth (7-7 in each arch). Three scores (according to the scale below) should be recorded buccally/labially (distal, body, mesial sites) and three scores lingually/palatally. All scorable teeth in one quadrant should be probed first (approximately 30 seconds) before recording the number of gingival units which bleed. The BI scoring system will be as follows:

0 = no bleeding after 30 seconds

1 = bleeding upon probing after 30 seconds

2 = immediate bleeding observed.

The study examiner will assess and record BI for each tooth site. The BI score for each subject will be calculated as the mean BI over all tooth sites. The primary endpoint is the BI score at Week 12.

4.4.1.2 Statistical Hypothesis, Model, and Method of Analysis

Summary statistics including mean, SD, SE, median, minimum, maximum will be provided by visit and randomized treatment group ([Table 14.2.1.2](#)). ANCOVA model will be applied to Week 12 BI score with treatment group, gender, smoking status and baseline MGI stratification as factors and baseline score as covariate. Adjusted means of two treatments and treatment difference will be provided together with 95%CI and P-values ([Table 14.2.1.1](#)).

4.4.1.3 Supportive Analyzes

The assumption of residual normality and variance homogeneity in ANCOVA analysis will be investigated through residual plots. If violated, data transformation or a nonparametric method (van Elteren test, adjusting for gender, smoking status and baseline MGI stratification) will be used. If the violation is caused by extreme values, a sensitivity analysis will be conducted by removing the extreme values. Nonparametric analysis, if performed, will be on change from baseline (as nonparametric analysis cannot incorporate continuous covariate). If nonparametric van Elteren test is performed and the inferences on treatment comparisons are similar to that of ANCOVA, both sets of results will be reported and the emphasis will be made on the ANCOVA results. Otherwise, nonparametric results will be used to draw conclusions.

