2. OBJECTIVES AND ENDPOINTS

Objectives	Endpoints
Primary	
To compare gingivitis, as measured by BI, following twice daily use of an experimental 0.454% w/w stannous fluoride dentifrice compared to a fluoride control dentifrice after 12 weeks twice daily use.	Mean BI at 12 weeks.
Secondary	
To compare gingivitis, as measured by the number of bleeding sites using BI, following twice daily use of an experimental 0.454% w/w stannous fluoride dentifrice compared to a fluoride control dentifrice after 12 weeks twice daily use.	Number of bleeding sites at 12 weeks.
To compare gingivitis, as measured by MGI, following twice daily use of an experimental 0.454% w/w stannous fluoride dentifrice compared to a fluoride control dentifrice after 12 weeks twice daily use.	Mean MGI at 12 weeks.
To compare dental plaque scores (PI; overall and interproximal) following twice daily use of an experimental 0.454% w/w stannous fluoride dentifrice to a fluoride control dentifrice after 12 weeks twice daily use.	Mean PI (overall and interproximal) at 12 weeks.
Other	
To compare gingivitis, as measured by BI, following twice daily use of an experimental 0.454% w/w stannous fluoride dentifrice compared to a fluoride control dentifrice after 6 weeks twice daily use.	Mean BI at 6 weeks.
To compare gingivitis, as measured by the number of bleeding sites using BI, following twice daily use of an experimental 0.454% w/w stannous fluoride dentifrice compared to a fluoride control dentifrice after 6 weeks twice daily use.	Number of bleeding sites at 6 weeks.
To compare gingivitis, as measured by MGI, following twice daily use of an experimental 0.454% w/w stannous fluoride dentifrice compared to a fluoride control dentifrice after	Mean MGI at 6 weeks.

Document Name	207014 protocol		
Type	Version	Document Identifier	Effective Date
eldo_clinical_doc	5.0; Most-Recent; Effective; CURRENT	090032d580d1fee8	05-Apr-2017 13:38:03
Reason For Issue			Auto Issue

6 weeks twice daily use.	
To compare dental plaque scores (PI; overall and interproximal) following twice daily use of an experimental 0.454% w/w stannous fluoride dentifrice to a fluoride control dentifrice after 6 weeks twice daily use.	Mean PI (overall and interproximal) at 6 weeks.
To evaluate and compare MGI and BI in low (≤ 2.00) and high (> 2.00) MGI subgroups following twice daily use of an experimental 0.454% w/w stannous fluoride dentifrice after 6 and 12 weeks twice daily use.	Mean MGI & BI at 6 & 12 weeks (in subgroups).

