9.2.4. Criteria for Assessing Efficacy

The success criterion of the study is to observe a statistically significant reduction in Bleeding Index in the test dentifrice group compared to the reference dentifrice group after 12 weeks of study treatments.

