9.3.2. Primary Analysis

Primary efficacy endpoint will be the Bleeding Index (BI) score after 12 weeks of study treatments. BI score will be calculated as the average index over all tooth sites. ANCOVA model will be applied for primary analysis with treatment, gender, smoking status and baseline MGI stratification as factors and baseline score as covariate. Adjusted means of two treatments and treatment difference will be provided together with 95%CI and P-values.

The assumption of residual normality and variance homogeneity in ANCOVA analysis will be investigated. If violated, data transformation or a non-parametric method will be used.

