9.3.3. Secondary Analyses

BI score at Week 6

BI score at Week 6 will be analysed using the same ANCOVA model as used for primary analysis.

Number of bleeding sites at Week 6 and Week 12

Number of bleeding sites will be calculated as the number of sites with a BI score of 1 or 2. At each post-baseline visit, number of bleeding sites will be analysed using ANCOVA model with treatment, gender, smoking status and baseline MGI stratification as factors and baseline score as covariate. Adjusted means of two treatments and treatment difference will be provided together with 95%CI and P-values.

MGI score at Week 6 and Week 12

MGI score will be calculated as the average index over all tooth sites. At each post-baseline visit, MGI score will be analysed using ANCOVA model with treatment, gender, smoking status as factors and baseline score as covariate. As baseline MGI is included as covariate, baseline MGI stratification will not be included again. Adjusted means of two treatments and treatment difference will be provided together with 95%CI and P-values

Overall plaque score at Week 6 and Week 12

Overall plaque score will be calculated as the average index over all tooth sites. At each post-baseline visit, overall plaque score will be analysed using ANCOVA model with treatment, gender, smoking status and baseline MGI stratification as factors and baseline score as covariate. Adjusted means of two treatments and treatment difference will be provided together with 95%CI and P-values.

Interproximal plaque score at Week 6 and Week 12

Document Name	207014 protocol		
Type	Version	Document Identifier	Effective Date
eldo_clinical_doc	5.0; Most-Recent; Effective; CURRENT	090032d580d1fee8	05-Apr-2017 13:38:03
Reason For Issue	Auto Issue		

Interproximal plaque score will be calculated as the average index over interproximal sites. Interproximal plaque score will be analysed similarly as overall plaque score.

For all of the above secondary analyses, Normality assumptions in ANCOVA models will be checked and accounted for in the same way as for the primary variable.

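### The rank-test fallback for the primary endpoint fixes the baseline slope at 1 for a reason that is not generally true; adjusting it for baseline BI would protect power at low to moderate baseline correlation

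*SAP*

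**What the plan says.** The primary endpoint is mean BI at Week 12 (Protocol 2 and 9.3.2). SAP 4.4.1.2 analyses it by ANCOVA with treatment, gender, smoking status and MGI stratum as factors and baseline BI as covariate, so the baseline slope is estimated from the data. Protocol 9.2.4 sets a single success criterion: "The success criterion of the study is to observe a statistically significant reduction in Bleeding Index in the test dentifrice group", compared with the reference group at 12 weeks.

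If the assumptions fail, Protocol 9.3.2 says only: "If violated, data transformation or a non-parametric method will be used". SAP 4.4.1.3 adds detail. It names the van Elteren test over the gender, smoking and MGI strata, and then: "Nonparametric analysis, if performed, will be on change from baseline (as nonparametric analysis cannot incorporate continuous covariate". If that test and the ANCOVA lead to similar inferences, both are reported with emphasis on the ANCOVA. If not: "Otherwise, nonparametric results will be used to draw conclusions".

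**The concern.** An analysis of change fixes the baseline slope at 1, whereas the primary model estimates it. The only reason given for the switch is that a nonparametric analysis cannot take a continuous covariate. That describes the plain van Elteren test. It does not describe the wider class: one can regress Week 12 BI on baseline and apply the same stratified rank test to the residuals.

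The choice matters because of the decision rule. Where the two analyses agree, the conclusion is the same; where they differ, the rank test wins. So whenever it is run, the test in a section headed as supportive in effect settles the trial's success criterion. If rho is low to moderate, a real effect that the ANCOVA detects could be reported as not shown.

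**Working it through.** **Inputs from the documents.** Difference 0.08, SD 0.14, 56 per group, stated power at least 80% (Protocol 9.1, SAP 1.4); two-sided 0.05 (SAP 4.4); eight strata (SAP 3.2).

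**Assumed, because not visible.** Rho, skewness, baseline SD, stratum sizes, and whether 0.14 is the SD at Week 12, the SD of change or the ANCOVA residual SD.

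**1. The plan's own figure.** 0.08 / (0.14 × √(2/56)) = 0.08 / 0.02646 = 3.02; 3.02 − 1.96 = 1.06; Φ(1.06) ≈ 85.6% (85.0% with the noncentral t). The stated power is met.

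**2. Normal theory, SD s at both visits.**
- SD of change = s√(2(1 − rho)); ANCOVA residual SD = s√(1 − rho²).
- Variance ratio = 2/(1 + rho), so 112 subjects analysed on change are worth 112 × (1 + rho)/2 on ANCOVA: 73, 84 and 95 at rho 0.3, 0.5 and 0.7.
- With s = 0.14 at rho 0.3, the SDs are 0.1657 (change) and 0.1336 (ANCOVA), giving power of 72.4% against 88.7%. At rho 0.5 it is 85.6% against 93.7%; at 0.7, 97.4% against 98.9%.
- Power on change falls below 80% when rho is below about 0.42.

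**3. Simulated power if the fallback is run.** Shifted lognormal data, SD 0.14 at both visits, additive effect 0.08, 56 per arm, assumed strata of 8/8/17/17/2/2/29/29, 20,000 runs per cell. The residual version fits baseline BI, gender, smoking and MGI stratum without treatment, and pools the two smallest strata over smoking.

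| rho | skewness | van Elteren on change | ANCOVA | van Elteren on residuals |
|---|---|---|---|---|
| 0.3 | 0.8 | 70% | 87% | 88% |
| 0.3 | 1.5 | 77% | 88% | 94% |
| 0.5 | 0.8 | 84% | 93% | 93% |
| 0.5 | 1.5 | 90% | 93% | 97% |
| 0.7 | 0.8 | 97% | 99% | 99% |
| 0.7 | 1.5 | 98.5% | 98.5% | 99.5% |

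Repeat runs agreed closely; their lowest values on change were 69% (rho 0.3) and 83% (rho 0.5). The residual test was never below the test on change in any cell computed. Pooling is not the cause: unpooled at rho 0.3 it gives 88.4% and 94.1%.

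**4. Other readings of 0.14.** If it is the SD of change, the SAP test has 84% power (skewness 0.8) or 89–91% (1.5) and does not fall below 80%. If it is the residual SD, normal-theory power on change is 68.4%, 74.5% and 79.6% at rho 0.3, 0.5 and 0.7, against 85.6% for ANCOVA.

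**5. How often the conclusion changes.**
- If the fallback were always run, ANCOVA would be significant and the fallback not in 14–19% of trials at rho 0.3. The reverse would occur in 2–3.5%.
- The SAP gives no numerical trigger. With Shapiro-Wilk p < 0.01 as a stand-in, at rho 0.3 it fires in about 39% of trials (skewness 0.8) or 86% (1.5). The loss then occurs in about 8–12% of trials at rho 0.3 (a repeat run gave 7.0% and 11.5%), 4% at 0.5 and 0.5% at 0.7.
- Whole-procedure power with the SAP test at rho 0.3/0.5/0.7 is 82/91/98% (skewness 0.8) and 79/90/99% (1.5).

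**6. False positives.** With equal arm distributions all three tests hold about 5%. With skewness 1.5, arm SDs differing 1.5-fold and equal means, rejection is about 10% for the residual test, 7–8% for the SAP test and 5% for ANCOVA.

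**The case against.** Much of the case on the other side stands.

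- **The fallback is conditional.** It needs a declared violation, and the rank route chosen over a transformation. The 14–19% figure is therefore not the risk for the trial as planned.
- **The planned power is not refuted.** A reader might infer from step 3 that the study has less than its stated 80%. The documents do not support that: the ANCOVA calculation is correct, and whole-procedure power is about 79% or more under these assumptions. Nothing in the documents shows that rho is low.
- **Change is not always the weaker choice against ANCOVA.** With strong skew (3.7) the SAP test beats ANCOVA, 95–100% against 88–98% at rho 0.3 to 0.7. The fair comparator is the baseline-adjusted rank test.
- **The parenthesis is true of the one test named.** The alternative also relies on a least-squares fit first. What fails is the general statement used to rule out adjustment.
- **The endpoint is not really abandoned.** A reader might say that a test of change leaves Week 12 BI. Under randomization an additive effect is the same on both, the SAP's null hypothesis is simply no difference between groups, and Protocol 9.3 leaves detail to the SAP.
- **The secondary endpoints.** Protocol 9.3.3 says "Normality assumptions in ANCOVA models will be checked and accounted for in the same way as for the primary variable". A reader might infer that the change-score rule extends to them. But Protocol 9.3.2 mentions neither change nor an overrule, and SAP 4.5 and 4.6 contain no fallback, so that reach is inference only.

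**Conclusion.** The point holds as a modest improvement to the SAP. The stated reason for using change is too broad, and a baseline-adjusted version of the same test is available. If the fallback is run, with SD 0.14 at both visits and skewness 0.8 to 1.5, the choice costs roughly 17–19 points of power at rho 0.3 (69–77% against 88–94%), 7–10 points at rho 0.5 (83–90% against 93–97%), and almost nothing at 0.7. The loss disappears as a threat to 80% power if 0.14 is the SD of change. These sizes rest on assumed values and are a range, not a prediction.

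A reader might go further and conclude that the ANCOVA should decide in every case. The documents do not settle that. It would depart from Protocol 9.3.2, which says another method will be used if assumptions fail, and it gives up power under strong skew. It is a trade-off for the sponsor.

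**What to change.** In SAP 4.4.1.3, delete the parenthesis about continuous covariates and define the variable for the van Elteren test as: *residuals from a regression of Week 12 BI on baseline BI, gender, smoking status and baseline MGI stratum, fitted without treatment*. Pool very small strata for this test, for example over smoking status where a stratum has fewer than 5 subjects or only one arm. Add that when the violation is unequal variance between arms, the rank result is reported but does not overrule the ANCOVA.

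The cost is SAP wording and a few lines of SAS, with no new data. Downsides to state:
- The test gives no adjusted mean difference.
- In normal data it is about 1–3 points below ANCOVA in power (up to 4 in one set of runs with other assumed strata).
- With skewed data and unequal arm SDs it rejects equal means in about 10% of trials (step 6), which is why the variance sentence is needed.

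SAP section 5 now declares no change from the protocol analysis. The variance sentence narrows the Protocol 9.3.2 rule and is best recorded there. If the sponsor prefers the ANCOVA to decide in all cases, an entry there is needed.
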